### 13.6.3 Assessment of Expectedness

- Expected** An adverse event, the nature or severity of which is consistent with the clinical condition of the participant.
- Unexpected** An adverse event, the nature or severity of which is not consistent with the clinical condition of the participant.

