Our Western Australian -based research team, through the *Missing Voices* project and a previous pilot study, was the first to investigate this issue across the state. This work involved an in depth epidemiological examination of the extent of acquired communication disorders (ACD) following brain injury and investigation into the experiences of individuals with ACD as well as health providers. We were the first to develop a screening tool for acquired communication disorders after brain damage in Aboriginal populations. Through interviewing brain injury survivors, their families, and a range of Aboriginal and non-Aboriginal health service providers, *Missing Voices* found that survivors and their families wanted more services, and found the transition from hospital to home difficult. Many felt they received little information on how to live with the brain injury in the longer term, including what services and funding were available to meet their ongoing needs. Our extensive file audit in *Missing Voices*, combined with interview data, also revealed that lack of coordination between services was a major issue and while in hospital, few people saw an Aboriginal Health Liaison Officer or an interpreter when English was not their first language. Aboriginal brain injury survivors are more likely to suffer from multiple and serious co-morbidities than non-Aboriginal survivors, and are more likely to live in very remote and socioeconomically disadvantaged areas in WA. As a result, they are more likely to be admitted to regional or district hospitals as emergency admissions. Difficulties associated with subsequent transfers to unfamiliar metropolitan hospitals away from country, compound the situation. Patients are distanced from families who struggle to find the resources to travel to visit their relative while at the same time maintaining often complex family situations at home.

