#### **13.1 Definition of an Adverse Event (AE)**

An Adverse Event (AE) is any untoward medical occurrence in any participant involved in the study. It does not necessarily have to have a causal relationship to the study intervention. However, for the purposes of this study, only those events which are possibly, probably or definitely attributable to the intervention will be noted.

Examples of an AE **include**:

- Exacerbation of a chronic or intermittent pre-existing condition including either an increase in frequency and/or intensity of the condition.
- New conditions detected or diagnosed after involvement in the study even though it may have been present prior to the start of the study.

Examples of an AE **do not include** a/an:

- Medical or surgical procedure (e.g. endoscopy, appendectomy); the condition that leads to the procedure is an AE.
- Situations where an untoward medical occurrence did not occur (social and/or convenience admission to hospital).

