### 13.5 Prompt Reporting of SAEs to the Sponsor

Once an investigator or assessor becomes aware that an SAE has occurred in a study participant, he/she will immediately notify the sponsor by contacting the Project Manager via telephone. The SAE form must be completed as thoroughly as possible with all available details of the event, signed by the investigator (or appropriately qualified designee), and sent to the Project Manager within 24 hours of first becoming aware of the event.

If the investigator does not have all information regarding an SAE, ***he/she will not wait to receive additional information before notifying the Project Manager*** of the event and completing the form. The form will be updated when additional information is received.

The blinded assessor will always provide an assessment of causality at the time of the initial report as described in Section 13.6.2, "Assessment of Causality".

In accordance with local IEC requirements, the investigator must also notify their Ethics Committee of any SAEs according to the guidelines of the Ethics Committee.

Those adverse events that are **CAUSALLY** related to the study treatment, **AND** that are both **SERIOUS** and **UNEXPECTED** – see section 9.8.3) are subject to expedited reporting to the independent Data Safety Monitoring Committee (DSMC).

The investigator, and others responsible for participant care, should institute any supplementary investigations of serious adverse events based on their clinical judgement of the likely causative factors. This may include seeking further opinion from a specialist in the field of the adverse event. If a participant dies, any post-mortem findings may be requested by the Sponsor.

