### 13.6.2 Assessment of Causality

The blinded assessor is obligated to assess the relationship between study treatment and the occurrence of each AE/SAE. The blinded assessor will use clinical judgment to determine the relationship. Alternative causes, such as natural history of the underlying diseases, concomitant therapy, other risk factors, and the temporal relationship of the event to the treatment period will be considered.

The causal relationship to the study treatment assessed by the blinded assessor should be assessed using the following classifications:

- Not Related** In the Assessors opinion, there is not a causal relationship between the study product and the adverse event.
- Unlikely** The temporal association between the adverse event and study treatment is such that the study treatment is not likely to have any reasonable association with the adverse event.
- Possible** The adverse event could have been caused by the study treatment.
- Probable** The adverse event follows a reasonable temporal sequence from the time of study treatment, abates upon discontinuation of treatment and cannot be reasonably explained by the known characteristics of the study participant’s clinical state.
- Definitely** The adverse event follows a reasonable temporal sequence from the time of study treatment start or reappears when study treatment is reintroduced.

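### The expectedness test in 13.6.3 is set against the participant's illness, so a related serious event can miss expedited DSMC reporting; separately, the causality grades in 13.6.2 are out of order

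*Protocol*

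**What the plan says.** **Routing.** Protocol Section 13.5 reserves expedited reporting to the independent DSMC for events that meet three conditions together: causally related to the study treatment, serious, and unexpected. For the meaning of unexpected it tells the reader to "see section 9.8.3". Section 9 is Participant Recruitment and has no subsections; the definition stands in Section 13.6.3.

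**Expectedness.** Section 13.6.3 defines Expected as "An adverse event, the nature or severity of which is consistent with the clinical condition of the participant" and Unexpected as "An adverse event, the nature or severity of which is not consistent with the clinical condition of the participant". Neither definition mentions the intervention.

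**Causality.** Section 13.6.2 has five grades. Probable requires a reasonable temporal sequence, and also that the event "abates upon discontinuation of treatment and cannot be reasonably explained by the known characteristics" of the participant's clinical state. Definitely reads: "The adverse event follows a reasonable temporal sequence from the time of study treatment start or reappears when study treatment is reintroduced". A preamble to the grades asks for clinical judgement and for alternative causes, including the natural history of the disease, to be considered.

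**Which grades count.** Section 13.5 names no grade at which an event becomes causally related. For the recording of adverse events, Section 13.1 pools three grades: "only those events which are possibly, probably or definitely attributable to the intervention will be noted".

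**Other routes.** Under Section 13.5 every SAE is telephoned to the Project Manager at once, with a form within 24 hours, and is notified to the ethics committee under that committee's guidelines. The synopsis has the safety committee review all events regularly, and Section 16.4.2 (Interim analyses) has the DSMC review interim AE and SAE data.

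**The concern.** Whether an event fits the participant's illness is a question about cause, and the Section 13.6.2 preamble already asks it. Section 13.6.3 asks it again under the name of expectedness. An event that has been attributed to the intervention can then be turned away from the prompt independent route for a reason unrelated to the intervention.

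The population makes this more than theoretical. Participants have had a recent stroke or traumatic brain injury, and Section 3 describes Aboriginal survivors as "more likely to suffer from multiple and serious co-morbidities than non-Aboriginal survivors". Many serious events could be said to fit such a picture. At stake is how soon the independent committee sees an individual serious event that someone believes the intervention caused.

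The causality scale is a second, separate problem. If the top grade is easier to meet than the one below it, the recorded grade does not tell the reader how strong the evidence of causation was.

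**Working it through.** No sample size, error rate or event count is involved, and the plan gives no figure to reproduce. The definitions can be checked as logical conditions.

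**1. The expedited test.** Expedited = related AND serious AND unexpected (Section 13.5). Failing any one condition removes the event from this route. Take an SAE graded as related whose nature and severity both fit the participant's condition. Under Section 13.6.3 it is Expected, so it is not expedited. Section 16.4.2 (Interim analyses) itself names death from all causes and aspiration pneumonia as SAEs for the DSMC; either can fit acute brain injury, depending on the participant.

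**2. Overlap of the two categories.** Both definitions join nature and severity with *or*. There are 2 × 2 = 4 combinations:

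| Nature fits condition | Severity fits condition | Meets Expected | Meets Unexpected |
|---|---|---|---|
| yes | yes | yes | no |
| yes | no | yes | yes |
| no | yes | yes | yes |
| no | no | no | yes |

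Two of the four meet both definitions, so for those events the test gives no determinate answer. An event of a familiar kind but of surprising severity is the obvious case.

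**3. Order of the causality grades.** Let T = reasonable temporal sequence, A = abates on discontinuation, N = not explained by clinical state, R = reappears on reintroduction (all from Section 13.6.2).

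- Probable = T and A and N.
- Definitely = T or R.

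Four yes/no conditions give 2⁴ = 16 combinations.

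- Probable fixes T, A and N and leaves R free: 2 combinations.
- Definitely holds whenever T is true (8 combinations), or when T is false and R is true (4 combinations): 8 + 4 = 12.

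Every combination that meets Probable has T true and so also meets Definitely; the reverse does not hold. Timing alone satisfies the top grade. Condition A cannot be met by an irreversible event such as death, and it has little meaning for staff training, which is not withdrawn from a participant.

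**4. How the two parts meet.** Because Probable requires N, an event so graded will usually be Unexpected and so be expedited. Possible and Definitely carry no such requirement. A serious event with the highest causality grade can therefore be Expected and miss the route, while one graded a step lower mostly will not. It is the expectedness wording that stops the event: Section 13.5 sets no grade cut-off, so the order of the grades does not decide routing.

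**The case against.** Much of the case on the other side stands, and it limits what can be claimed.

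- **Other routes exist.** A reader might infer that related serious events are kept from the DSMC. The protocol does not support that. All SAEs reach the Project Manager within 24 hours whatever their expectedness, they go to the ethics committee under its guidelines, and the DSMC reviews events periodically. What can be lost is time.
- **The inverted scale filters nothing.** A reader might infer that it too removes events from expedited reporting. It does not, since Section 13.5 asks only for a causal relationship and Section 13.1 pools the grades from possible upward.
- **The preamble tempers the grades.** An assessor who follows Section 13.6.2 as a whole should not grade a natural-history event Definitely on timing alone. The literal wording would allow it; that it would happen is not shown. The preamble softens the grade definitions but does not repair them.
- **The statistical safety analyses do not use the grades.** A reader might infer distorted tables of related events, but the protocol specifies none. Section 16.4.2 compares counts of serious adverse events and binary events such as death between conditions, and its Haybittle-Peto boundary (at least 3 standard errors) is applied to serious adverse events. Neither is restricted by causality.
- **Expectedness is judged case by case.** It would go too far to say that every death or pneumonia must be Expected. The trial admits any NIHSS above 0 and excludes palliative patients not likely to survive to 26 weeks, so death in a mildly affected participant may well not fit that person's condition.
- **Stakes and unseen documents.** The intervention is training, support and advocacy, so few SAEs are likely to be attributed to it. Sections 11 and 21.1 refer to an Intervention Protocol and to Monitoring Guidelines that are not at hand and may add to these rules.

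None of this changes what Sections 13.5 and 13.6.3 say: the protocol creates a prompt independent route and then defines entry to it by the wrong yardstick.

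**Conclusion.** The point holds as a defect of wording with a limited practical effect. The expectedness definition can delay DSMC sight of a serious event already attributed to the intervention when that event also fits the participant's illness. The two categories overlap in two of four combinations. The grade Definitely is logically looser than Probable, by 12 combinations to 2 of 16, which makes the grades unreliable without altering routing. The reference to Section 9.8.3 is an editorial slip with an evident target.

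The combination counts show how the rules are ordered; they are not frequencies of events. How many events would be affected cannot be derived from the protocol; the number is probably small. The conclusion assumes that Sections 13.5 and 13.6 are applied as written and that no unseen document overrides them. These are working definitions for assessors and sites, so they belong in the protocol and are not a matter to leave to an SAP.

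**What to change.** - **Section 13.6.3:** define expectedness by reference to the foreseen effects of the intervention, listed in the protocol or in a document it names. If none are listed, treat a related SAE as unexpected. Make the categories exclusive, for example by requiring both nature and severity to match for Expected and assigning everything else to Unexpected.
- **Section 13.6.2:** make Definitely at least as strict as Probable, including that the participant's clinical state does not explain the event. Replace the discontinuation and reintroduction criteria with ones that can be applied to irreversible events and to a staff-training intervention.
- **Section 13.5:** state which grades count as causally related, and change the cross-reference from 9.8.3 to 13.6.3.
- **SAE form:** carry the same definitions.

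The cost is an amendment to the wording and the form, and a few more expedited reports to the DSMC. No analysis, sample size or visit schedule changes.

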## 13.7 Follow-up of AEs and SAEs

After the initial AE/SAE report, the investigator is required to proactively follow each participant and provide further information to the sponsor for all ongoing events.

All AEs and SAEs documented at a previous visit/contact and are designated as ongoing, will be reviewed at subsequent visits/contacts.

All AEs and SAEs will be followed until resolution, until the condition stabilises, until the event is otherwise explained, or until the participant is lost to follow-up.

New or updated information will be recorded on the originally completed SAE form, with all changes signed and dated by the investigator. The updated SAE form should be resent to the Sponsor.

## **14 Participant Completion and Discontinuation**

### **14.1 Participant Completion**

Participants have completed the study when the final follow up visit at week 26 is complete and all data pertaining to this visit has been submitted to the study Sponsor.

### **14.2 Participant Withdrawal**

Participants will be withdrawn from the study if they withdraw consent to continue, or if it is determined that involvement in the trial poses a health or safety risk to the participant.

Data collected up until the time of withdrawal will be used in analysis unless otherwise requested by the participant.

Withdrawn participants will not be replaced.

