### **13.3 Time Period, Frequency, and Method of Detecting AEs and SAEs**

All SAEs will be recorded from the time of consent until the final follow up visit at week 26.

Other adverse events possibly, probably, or definitely attributable to the intervention will be recorded from the time of consent until the final follow up visit at week 26.

Each participant will be monitored regularly by the site investigator and study personnel for events occurring throughout the study. During the period in hospital, the site investigator will enquire about AEs by asking the following non-leading questions:

*“How are you feeling?”*

At subsequent scheduled intervals participants will be asked:

*“Since you were last asked, have you felt unwell or different from usual?”*

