### **16.4 Statistical Analyses**

The primary analysis will be performed on an intention to treat basis with each participant allocated to the site at which he/she was originally recruited.

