#### **16.4.1 Primary outcome analysis**

The primary hypothesis (H1) will be analysed using a mixed effects linear regression model, which controls for the effects of secular trends over time. The model will be designed to assess the effect of the intervention on Euro QOL–5D-3L VAS score at 26 weeks post injury. Differences in baseline characteristics will be included in the model.

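### Section 14.2 merges stopping coordinator contact with leaving the study, so participants withdrawn on safety grounds lose the week-26 VAS and later SAE recording even if they still consent to follow-up

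*Protocol*

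**What the plan says.** Protocol section 14.2 has a single way out. A participant is withdrawn from the study on withdrawing consent, "or if it is determined that involvement in the trial poses a health or safety risk to the participant". After that, "Data collected up until the time of withdrawal will be used in analysis unless otherwise requested by the participant", and "Withdrawn participants will not be replaced". Neither this section nor any other describes a participant whose coordinator contact has stopped but whose assessments go on.

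Other sections assume observation to week 26:

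- Section 13.3: "All SAEs will be recorded from the time of consent until the final follow up visit at week 26".
- Section 13.7: "All AEs and SAEs will be followed until resolution, until the condition stabilises, until the event is otherwise explained". The same sentence adds loss to follow-up as a further end point.
- Section 16.4: "The primary analysis will be performed on an intention to treat basis with each participant allocated to the site" of original recruitment.
- Section 16.4.1: the model estimates the effect on the "VAS score at 26 weeks post injury. Differences in baseline characteristics will be included in the model".
- Section 16.4.2, Safety: SAE counts are compared between the intervention and control conditions.

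The EQ-5D-3L, which contains the VAS, is collected at weeks 12 and 26 only (section 10.3.1, Appendix 1). The mRS, FIM and HADS are also collected at baseline.

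**The concern.** Two different events share one rule. One is that contact with the Aboriginal Brain Injury Coordinator stops. The other is that the participant leaves follow-up. Applied as written, a judgement that coordinator contact is a risk also ends the week-12 and week-26 assessments and the recording of new SAEs, although the participant, or their Research Decision Maker, may still agree to both.

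The people lost are selected on safety grounds, so their missing week-26 scores are unlikely to resemble those observed. The loss may also be uneven. Control participants have assessments and service-data collection; intervention participants have coordinator contact as well, for up to 26 weeks (section 11.1.2). The Blinding paragraph of 16.4.2 concedes that assessors, patients and most investigators cannot be blinded to intervention status, so the judgement would often be made knowing the condition. If such withdrawals fall mainly in the intervention phase, the VAS comparison could favour the intervention and its later SAEs could be undercounted.

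**Working it through.** **The sections side by side.** Section 13.3 records all SAEs to the final visit at week 26; section 14.2 takes the participant out of the study before then. Section 16.4.1 needs a VAS at week 26; after a 14.2 withdrawal none is provided for. Because the VAS is absent at baseline, withdrawal before week 12 leaves no VAS at all, while withdrawal after week 12 leaves one. How missing values are handled may be left to the SAP, but an SAP cannot restore data that the protocol stops collecting.

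**The plan's own figure.** Section 16.3 gives a 15-point difference, an SD of 25, 80% power and 5% significance, so d = 15/25 = 0.6. A two-sided two-sample t-test needs 44.59 per group, rounded up to 45, or 2 × 45 = 90. This matches the stated 90 before the design effect. Fifteen points is therefore the yardstick below.

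**Inputs not in the documents (assumptions).**

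- w: share of intervention participants withdrawn for safety.
- g: how far their unobserved week-26 VAS lies below that of those who remain.
- r: their SAE rate relative to the others.
- They lose half of their SAEs through early withdrawal.
- There are no such withdrawals under control, and no correction by the model.

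**VAS.** Let the observed intervention mean be m. The full mean is (1 − w)m + w(m − g) = m − wg, so the bias is w × g in favour of the intervention. Examples: 0.01 × 10 = 0.1; 0.05 × 30 = 1.5.

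**SAE counts.** Observed/full = (1 − w + 0.5wr) / (1 − w + wr). Example with w = 5% and r = 3: (0.95 + 0.075) / (0.95 + 0.15) = 1.025/1.10 = 0.932.

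| w | VAS bias, g = 10 to 30 | Observed/full SAEs, r = 1 to 3 |
|---|---|---|
| 1% | 0.1 to 0.3 | 0.995 to 0.985 |
| 2% | 0.2 to 0.6 | 0.990 to 0.971 |
| 5% | 0.5 to 1.5 | 0.975 to 0.932 |
| 10% | 1.0 to 3.0 | 0.950 to 0.875 |

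At 5% the largest VAS bias is 1.5/15 = 10% of the target. The 10% row is an upper stress case. If control participants were withdrawn as well, at rate w₀ with the same deficit, the net bias would shrink to (w − w₀) × g.

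**The case against.** Much can be said for the plan, and most of it limits the size of the problem.

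- **Trigger.** A reader might infer that follow-up ends for exactly those who are harmed. It does not. The trigger is a judgement that involvement poses a risk; an AE or SAE alone does not remove anyone.
- **Section 13.7.** A reader might see a flat contradiction. The sentence also allows follow-up to end at loss to follow-up, and nothing exempts withdrawn participants from follow-up of events already reported. An SAE recorded before withdrawal stays in the count. What is at risk is new, later SAEs.
- **Intention to treat.** Section 16.4 explains this as allocation to the recruiting site, and 14.2 neither reallocates nor excludes anyone. It creates missing outcomes, which is a tension with the aim and not a breach of the stated definition.
- **Phase.** The text of 14.2 covers both phases. That withdrawals would occur almost only under intervention is an inference. It is reasonable for the coordinator component, but staff training is not an individual exposure and assessments occur in both phases.
- **Modelling.** Week-12 VAS, where available, and baseline mRS, FIM and HADS give partial support to a model for the missing scores.
- **Frequency.** Sections 9 and 21.3 describe the intervention as support and monitoring. Safety withdrawals are probably rare, and no section gives a rate.

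All of this stands. None of it supplies a route by which a still-consenting participant whose coordinator contact has stopped keeps the remaining assessments and SAE recording.

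**Conclusion.** The defect is one of structure: section 14.2 treats the end of the intervention as the end of observation. It conflicts most clearly with SAE recording to week 26 in 13.3, and it weakens the intention-to-treat estimate of the week-26 VAS and the SAE comparison.

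The consequence is possible bias, not demonstrated bias. Under assumed safety withdrawals of 1 to 5%, confined to the intervention condition, with deficits of 10 to 30 points and no model correction, the VAS difference would be overstated by about 0.1 to 1.5 points of the 15-point target. Observed intervention SAE counts would be about 0.995 to 0.93 of the full count. The documents do not support a claim that the trial's result is biased by a known amount, or that the loss is confined to one phase. The point merits a change because the data are already scheduled and cannot be recovered later, not because the expected bias is large.

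**What to change.** In section 14.2, distinguish two events: stopping coordinator contact, and withdrawal from follow-up. Where only coordinator contact stops and the participant or their Research Decision Maker still consents, state that the week-12 and week-26 assessments, SAE recording and the file audit of section 10.4 continue, and that these data enter the intention-to-treat analysis.

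Leave the sponsor's existing criterion for ending contact as it is, and keep the existing exit where the assessments themselves are judged a risk. Withdrawal of consent should not become the only way out of follow-up; when a participant should stop contact or leave is not at issue here.

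Reconcile 14.2 with 13.3, 13.7, 14.1 and 16.4, including what 13.7 means for events still open at withdrawal.

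The cost is protocol wording, one CRF field that records which of the two events occurred and when, and a few follow-up contacts already scheduled for every participant.
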